## Appendix G. Definition of Additional Safety Topics

Additional Safety Topics will be identified by the following CMQ, SMQ, or other search criteria:

Additional safety topics	Search criteria
Anaphylactic reactions	Narrow SMQ "anaphylactic reactions" (20000021)
Hypersensitivity reactions	Narrow SMQ "hypersensitivity" (20000214)
Injection site reactions	CMQ "Injection site reaction" (10000091)
Suicidal ideation and behavior	Narrow SMQ "Suicide/self-injury" (20000037)
Conjunctivitis	Narrow SMQ "Conjunctival disorders" (20000175)
Keratitis	Including the following PTs: 
 
• Allergic keratitis
 
• Infective keratitis
 
• Keratitis
 
• Keratitis bacterial
 
• Keratitis fungal
 
• Keratitis interstitial
 
• Keratitis sclerosing
 
• Keratitis viral
 
• Punctate keratitis
 
• Ulcerative keratitis
 
• Varicella keratitis
 

Additional safety topics	Search criteria
Parasitic (Helminth) Infections	Including the following PTs: 
 
• Arthritis helminthic
 
• Biliary tract infection helminthic
 
• Cystitis helminthic
 
• Endocarditis helminthic
 
• Enterocolitis helminthic
 
• Eye infection helminthic
 
• Gastritis helminthic
 
• Genital infection helminthic
 
• Helminthic infection
 
• Hepatic infection helminthic
 
• Lymphadenitis helminthic
 
• Meningoencephalitis helminthic
 
• Myocarditis helminthic
 
• Oral helminthic infection
 
• Pancreatitis helminthic
 
• Pericarditis helminthic
 
• Pneumonia helminthic
 
• Skin infection helminthic
 
• Splenic infection helminthic
 
• Upper respiratory tract infection helminthic
 
• Vulvovaginitis helminthic
 
• Wound infection helminthic
 

Arthralgia	Including PT arthralgia

## **Appendix H. Non-Responder Imputation Incorporating Multiple Imputation to Handle Missing Data Due to COVID-19 Pandemic or Any Other Missing Data That Can Be Reasonably Assumed to Be Missing at Random for Dichotomized Outcome Variables**

### **1.0 Overview**

#### **1.1 Background and Justification for Missing at Random (MAR) Assumption**

The COVID-19 pandemic is interfering with the conduct of many ongoing trials, with potential impacts on treatment duration and the collection, analysis and the interpretation of clinical trial data. Some protocol-specified visits in the clinical trials may be impacted due to COVID-19 infection or logistical restrictions during the pandemic. For example, some scheduled visits may be missed due to self-quarantine or local government restrictions on travel; some visits may also be delayed or canceled due to healthcare resource constraints during the pandemic. Impacted visits due to COVID-19 will be recorded in the database. The probability of having missed visits and missing data due to COVID-19 infection or logistical restrictions related to the COVID-19 pandemic can be reasonably assumed to be unrelated to the unobserved values. Therefore, for the purpose of statistical analysis, it is reasonable to assume that these missing data are missing at random (MAR) and the statistical models that require MAR assumption are appropriate. In some cases, sensitivity analyses may be performed to assess the impact of missing data and the robustness of the conclusion.

#### **1.2 FDA Guidance**

FDA provided two guidance documents in March 2020 and June 2020 on the efficacy collection and possible changes in the statistical analysis plan:

"With respect to efficacy assessments, FDA recommends consultation with the appropriate review division regarding protocol modifications for the collection of efficacy endpoints, such as use of virtual assessments, delays in assessments, and alternative collection of research-specific specimens, if feasible. For individual instances where

efficacy endpoints are not collected, the reasons for failing to obtain the efficacy assessment should be documented (e.g., identifying the specific limitation imposed by COVID-19 leading to the inability to perform the protocol-specified assessment)."

"If changes in the protocol will lead to amending data management and/or statistical analysis plans, the sponsor should consider doing so in consultation with the applicable FDA review division. Prior to locking the database, sponsors should address in the statistical analysis plan how protocol deviations related to COVID-19 will be handled for the prespecified analyses."

### **1.3 EMA Guidance**

EMA provided guidance in March 2020:

"At this point in time it is not possible to give general applicable advice on how the different aspects related to the pandemic should be handled, as implications on clinical trials are expected to be manifold. Impact on the data collection, analysis and interpretation of results for each trial will need a thorough case-by-case assessment."

"As a general principle, there are strong scientific reasons to conduct trials as planned and implement changes only when there is a convincing scientific reason that it improves interpretability of results."

### **1.4 Missing Data Handling for Missing Due to COVID-19 or Any Other Missing Data That Can Be Reasonably Assumed to Be Missing at Random for Dichotomized Variables**

In this document, a missing data handling method is proposed to handle missing data due to COVID-19 infection or logistical restrictions related to the COVID-19 pandemic or any other missing data that can be reasonably assumed to be missing at random under the general MAR framework. In particular, we explain using multiple imputation (MI) to handle missing data due to COVID-19 or any other missing data that can be reasonably assumed to be Missing at Random in dichotomized variables in conjunction with non-responder imputation (NRI) for missing data due to other reasons.

## **2.0 Non-responder Imputation Incorporating Multiple Imputation (NRI-MI)**

### **2.1 Overall Description of the Method**

For a dichotomized outcome variable with missing data, the NRI-MI will categorize any subject who does not have evaluation during a pre-specified visit window as a non-responder for the visit, with two exceptions:

If the subject is a responder both before and after the pre-specified visit window in Period 1, the subject will be categorized as a responder for the visit.

If the reason for missing (e.g., missed visits, incomplete visit, out-of-schedule visits, or discontinuations of study drug) is due to COVID-19 or any other missing data that can be reasonably assumed to be Missing at Random, the information will be captured in the database and the subject's response status will be imputed using multiple imputation.

In addition, subjects whose change/percent change from Baseline cannot be calculated because of a missing Baseline will be considered as a non-responder at all post-baseline visits unless the post-baseline value is zero.

Non-responder imputation incorporating multiple imputation (NRI-MI) for missing due to COVID-19 or any other missing data that can be reasonably assumed to be Missing at Random will be implemented as follows.

### **2.2 Multiple Imputation (MI) and MAR Assumption**

When a dichotomized variable is derived from a continuous scale, for example, EASI 90 (at least a 90% reduction in EASI relative to Baseline), the multiple imputation will be applied to the original scale, EASI (ranges from 0 - 72) assuming multivariate normal distribution. Then the dichotomized variable will be derived from the imputed value.

The MI procedure assumes that the data are missing at random (MAR). That is, for an outcome variable Y, the probability that an observation is missing depends only on the

observed values of other variables, not on the unobserved values of the outcome variable Y. Statistical inference from the MI procedure is valid under the MAR assumption.

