### A. Random Seeds for NRI-MI

Endpoints	Random Seed	
	MCMC procedure	PROC MI
EASI 90 and WP-NRS 0/1 at Week 16 a	1001 for EASI 90; 1002 for WP-NRS	9001 for EASI 90; 9002 for WP-NRS
EASI 90 at Week 16	1003	9003
WP-NRS 0/1 at Week 16 among subjects with Baseline WP-NRS > 1	1004	9004
An improvement (reduction) in WP-NRS $\geq 4$ at Week 16 among subjects with Baseline WP-NRS $\geq 4$ b	1005	9005
WP-NRS 0/1 at Week 4 among subjects with Baseline WP-NRS > 1 c	1006	9006
WP-NRS 0/1 at Week 2 among subjects with Baseline WP-NRS > 1 d	1007	9007
EASI 90 at Week 4 e	1008	9008
EASI 75 at Week 2 a	1009	9009
EASI 100 at Week 16 a	1010	9010
Achievement of 75% reduction in EASI in the head and neck region from Baseline at Week 2, 4, 8, 12, 16	1011	9011
Achievement of 75% reduction in EASI in the trunk region from Baseline at Week 2, 4, 8, 12, 16	1012	9012

Endpoints	Random Seed	
	MCMC procedure	PROC MI
Achievement of 75% reduction in EASI in the upper extremities region from Baseline at Week 2, 4, 8, 12, 16	1013	9013
Achievement of 75% reduction in EASI in the lower extremities region from Baseline at Week 2, 4, 8, 12, 16	1014	9014

Notes:

- The random seed for the corresponding endpoint at the other visits (i.e., Week 2, 4, 8, 12) will use the random seed for that endpoint at Week 16, except EASI 75 where the random seed for this endpoint at the other visits (i.e., Week 4, 8, 12, 16) will use the one at Week 2.
- The random seed for an improvement (reduction) in WP NRS  $\geq 4$  at the other visits (i.e., Week 1, 2, 3, 4, 5, 6, 7, 8, 9, 10, 11, 12, 13, 14 and 15) will use the random seed for this endpoint at Week 16.
- The random seed for WP NRS 0/1 at Week 5, 6, 7, 8, 9, 10, 11, 12, 13, 14 and 15 will use the random seed for this endpoint at Week 4.
- The random seed for WP NRS 0/1 at Week 1 and 3 will use the random seed for this endpoint at Week 2.
- The random seed for EASI 90 at the other visits (i.e., Week 2, 8 and 12) will use the random seed for this endpoint at Week 4.

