### **Imputation Step**

For missing data with monotone missing patterns, the choice of multiple imputation using a parametric regression model that assumes multivariate normality is appropriate.

The imputation step is described below:

The imputation model for the missing data is a regression model, which controls for treatment, stratification factors (vIGA-AD categories [vIGA-AD 3; 4]) and age (12 to < 18; 18 to < 40;  $\geq$  40 to < 64 years), Baseline, and all post-baseline visits of the outcome variable. The covariates included in the model and the order of these variables are consistent with the augmentation step.

For each monotone missing dataset, using SAS PROC MI with MONOTONE REG model statement, the outcome variable at each post-baseline visit with missing values will be imputed sequentially with covariates constructed from their corresponding sets of preceding variables.

A 'complete' dataset with imputed values for the missing data is generated after the augmentation and imputation steps are completed.

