### 3.0 Sample SAS Code

```

/*****/
/*IMPUTATION ALGORITHM*/
/*****/
/*NOTE: THIS APPROACH REQUIRES NO MISSING IN CATEGORICAL COVARIATES AND
REQUIRES AT LEAST ONE OBSERVATION IN BASELIBE OR ONE OF THE POST
BASELINE VISIT*/

/*PRE AUGMENTATION CREATE DUMMY FOR CATEGORICAL VARIABLES*/
/*****/
DATA EASI_2; SET EASI;
  /*THE MCMC STATEMENT BELOW ASSUMES MULTI VARIATE NORMAL*/
  /*IF TREATMENT OR ANY COVARIATES ARE CATEGORICAL WITH L>2 LEVELS*/
  /*NEED TO CREATE L 1 DUMMY VARIABLES*/
  /*HERE, TREATMENT (TRT01PN) HAS 2 LEVELS, SO WE NEED 1 DUMMY
VARIABLES*/
  IF TRT01PN=1 THEN TRT1=1;
  ELSE TRT1=0;
RUN;

/*AUGMENTATION STEP TO HAVE 30 MONOTONE MISSING DATASETS*/
PROC MI DATA=EASI_2 OUT=EASI_MONO NIMPUTE=30 SEED= 1001 /*RANDOM SEED
PRE DEFINED*/
  ROUND=. . . 0.1 0.1 0.1 0.1 0.1 0.1 /*VALUE ROUND TO 1ST DECIMAL*/
  MIN=. . . 0 0 0 0 0 0 /*MINIMUM VALUE OF EASI IS 0*/
  MAX=. . . 72 72 72 72 72 72; /*MAXIMUM VALUE OF EASI IS 72*/
  MCMC IMPUTE=MONOTONE ;
/*NOTE: CATEGORICAL VARIABLES SUCH AS TRT1 ARE DUMMY, CREATED ABOVE*/
/*NOTE: ALL OTHER NON DUMMIED COVARIATES MUST BE CONTINUOUS*/
/*SUPPOSE STRATAN (NUMERIC VARIABLE FOR STRATA) HAS ONLY 2 LEVELS, NO
NEED TO CREATE DUMMY*/
  VAR TRT1 AGEGR1N VIGAGR1N BASE WK2 WK4 WK8 WK12 WK16;
/*CAUTION TO USE THE "BY" STATEMENT IN MCMC: */
/*MVN MODEL IS FITTED WITHIN EACH 'BY' GROUP, INSTEAD OF ACROSS ALL
GROUPS*/
RUN;

```

```

/*IMPUTATION STEP  DETERMINE IMPUTATION DISTRIBUTION AND RANDOMLY
IMPUTE MISSING VALUE TO GENERATE 'COMPLETE' DATASETS*/
/*****/
PROC MI DATA=EASI_MONO OUT=EASI_FULL NIMPUTE=1 SEED= 9001 /*RANDOM SEED
PRE DEFINED*/
  ROUND=. . . 0.1 0.1 0.1 0.1 0.1 0.1 /*VALUE ROUND TO 1ST DECIMAL*/
  MIN=. . . 0 0 0 0 0 0 /*MINIMUM VALUE OF EASI IS 0*/
  MAX=. . . 72 72 72 72 72 72; /*MAXIMUM VALUE OF EASI IS 72*/
  MINMAXITER=1000;
  CLASS TRT01PN AGEGR1N VIGAGR1N;
  VAR TRT01PN AGEGR1N VIGAGR1N BASE WK2 WK4 WK8 WK12 WK16;
  MONOTONE REG (WK2 WK4 WK8 WK12 WK16); /* IMPUTED SEQUENTIALLY, FROM
WK 2 TO 16, WITH COVARIATES CONSTRUCTED FROM THE CORRESPONDING PRECEDING
VARIABLES*/
  BY IMPUTATION ; /*FOR EACH OF THE 30 MONOTONE
MISSING DATASETS, IMPUTE A 'COMPLETE' DATASET*/
RUN;

/*DETERMINE DICHOTOMOUS RESPONSE STATUS, EASI 90*/
DATA ALL; SET EASI_FULL;
  IF 0<=WK2<=0.9*BASE THEN EASI90_2=1;
  ELSE EASI90_2=0;
  IF 0<=WK4<=0.9*BASE THEN EASI90_4=1;
  ELSE EASI90_4=0;
  IF 0<=WK8<=0.9*BASE THEN EASI90_8=1;
  ELSE EASI90_8=0;
  IF 0<=WK12<=0.9*BASE THEN EASI90_12=1;
  ELSE EASI90_12=0;

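### Where missing EASI is multiply imputed, a bounded normal model almost never yields EASI 100 and yields too few EASI 90 responders; the effect on treatment differences is small.

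*SAP*

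**What the plan says.** SAP Appendix H, 2.2, sets the scale and distribution: "the multiple imputation will be applied to the original scale, EASI (ranges from 0 - 72) assuming multivariate normal distribution". It continues: "Then the dichotomized variable will be derived from the imputed value". The Imputation Step in Appendix H, 2.3, defends the model: "the choice of multiple imputation using a parametric regression model that assumes multivariate normality is appropriate". The sample code in Appendix H, 3.0, implements it as "MONOTONE REG (WK2 WK4 WK8 WK12 WK16" with bounds of 0 and 72 ("MINIMUM VALUE OF EASI IS 0"), rounding to 0.1 and "MINMAXITER=1000". Intermittent gaps are filled beforehand by an MCMC step that makes the same normality assumption.

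The seed table in SAP Appendix D shows that the method serves the ranked EASI endpoints, including "EASI 100 at Week 16", and regional EASI.

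Two limits on scope matter. In the main Period 1 analysis (SAP 9.2 and Appendix H, 2.4), MI covers only gaps due to COVID-19 or otherwise judged missing at random; other gaps, and visits after rescue, count as non-response. A full MI analysis is planned as a sensitivity analysis of the primary endpoint only (SAP 9.3.3), and there too rescued subjects stay non-responders.

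**The concern.** EASI on effective treatment is expected to pile up near 0, with some subjects exactly at 0. A normal regression on the raw score has no point mass at 0 and spreads probability across the range. Dichotomising its draws can therefore give wrong response rates even when the data really are missing at random. Appendix H, 2.2, presents validity as following from the MAR assumption, but validity also needs an imputation model that reproduces the response rate near the cut-off. The SAP plans no transformation, distributional check or alternative model.

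At stake are the imputed part of the primary endpoint and of the EASI-based ranked endpoints, including EASI 100, which is last in the alpha-controlled hierarchy. Also at stake is how much independent information the MI sensitivity analysis adds: it shares the model and leans toward NRI.

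**Working it through.** **Inputs from the documents.** Normal model on raw EASI, range 0-72, rounding to 0.1 (SAP Appendix H). EASI 90 in the text is at least a 90% reduction. Baseline EASI is at least 16 (Protocol 5.1), so the lowest EASI 90 cut-off is 0.1 × 16 = 1.6. There are 440 subjects per arm, with assumed primary response of 12% on dupilumab and 12 + 17 = 29% on upadacitinib (SAP 2.4).

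**Assumed, because the documents are silent.** The EASI distribution, visit correlation and missing rate. I also take it that out-of-range draws are redrawn, as the code's bounds and iteration limit imply.

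**1. The plan's own figure.** SE = √[(0.29×0.71 + 0.12×0.88)/440] = 0.0266. Then 0.17/0.0266 = 6.39 and power = Φ(6.39 − 1.96), above 99.9%. The stated power of more than 90% is reproduced.

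**2. EASI 100, exact.** The draw must fall in [0, 0.05). For a normal with mean m and SD s truncated to 0-72, the probability is [Φ((0.05−m)/s) − Φ(−m/s)] / [Φ((72−m)/s) − Φ(−m/s)]:

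| Mean | SD 3 | SD 4 | SD 10 |
|---|---|---|---|
| 0 | 1.3% | 1.0% | 0.4% |
| 4 | 0.3% | 0.4% | 0.3% |
| 8 | 0.02% | 0.07% | 0.2% |

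At SD 1.5 the maximum is 2.7%, at mean 0. The true EASI 100 rate does not enter except through m and s.

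**3. Simulation, 40,000 per arm.** Week 16 EASI was skewed with a point mass at 0, and 10% were missing at random. Imputation was by sequential normal regression on treatment, a severity proxy, Baseline and earlier visits; parameter-draw uncertainty was ignored.

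- EASI 100: imputed 0.0-1.0% in every redraw scenario, against true rates of about 7-23% (upadacitinib) and 2-9% (dupilumab).
- EASI 90, text cut-off, mid-range case (residual SD 3.7-5.7), upadacitinib: imputed 14-25%, true 44-46%.
- EASI 90, all scenarios: imputed/true from about 14% to 89%, a shortfall of 86% to 11%. In the mildest case (residual SD 1.3, only Week 16 missing), upadacitinib was imputed 41% against 47% true.
- Predictive mean matching, true rates about 45%/25% (EASI 90) and 15%/5% (EASI 100): imputed 44-47%/24-27% and 14-17%/4-5%. The shortfall disappears.

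A separate simulation at trial size (440 per arm; assumed EASI 100/90 of 16/43% and 7/30%; Week 12 observed) gave imputed against true EASI 90 of 24% vs 42% (upadacitinib) and 19% vs 31% (dupilumab). For EASI 100 it gave 0.4% vs 16.5% and 0.3% vs 7.3%.

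**4. Effect on the treatment difference.** Bias = f_U × (imputed − true)_U − f_D × (imputed − true)_D, where f is the fraction imputed in each arm.

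- EASI 90, f = 10% in both arms. Trial-size simulation: 0.10 × [(24−42) − (19−31)] = −0.6 points. Large simulation, true 45/25: imputed 25/16 gives 0.10 × (−20 + 9) = −1.1; imputed 14/9 gives 0.10 × (−31 + 16) = −1.5. At 3% imputed the last two become −0.3 and −0.5. NRI at 10% would give −0.10 × 20 = −2.0.
- EASI 100, f = 10%: 0.10 × [(0.4−16.5) − (0.3−7.3)] = −0.9 points.
- EASI 90, unequal, 1% upadacitinib and 10% dupilumab, imputed 14/9: 0.01 × (−31) − 0.10 × (−16) = +1.3 points, in favour of upadacitinib.

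**5. Effect on power** (unadjusted, same formula as step 1, trial-size rates, 10% imputed).

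- EASI 100: 0.9×16 + 0.1×0.4 = 14.4% vs 0.9×7 + 0.1×0.3 = 6.3%. Power falls from 98.8% to 97.8%.
- EASI 90: 0.9×43 + 0.1×24 = 41.1% vs 0.9×30 + 0.1×19 = 28.9%. Power falls from 98.1% to 96.9%.
- Primary, even if all 10% in both arms were non-responders: 26.1% vs 10.8%. Power stays above 99.9%.

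**6. The sample code's cut-off.** It scores EASI 90 when the value is at most 0.9 × Baseline, a 10% reduction, which contradicts the text. Run as written, 60-91% of imputed subjects count as responders, so the error reverses.

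**The case against.** The strongest reply is that little of this reaches a result. In NRI-MI only gaps flagged as missing at random are imputed, the documents predict no missing rate, EASI 100 ranks last, and the planned NRI analysis lowers the EASI 90 difference by more than this error does. Steps 4 and 5 bear this out, and it stands.

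A reader might infer four stronger things, none of which the documents support.

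- That EASI 90 is under-imputed by a known, large amount. The direction is firm under the text definition. The size depends on an EASI distribution and visit correlation not given, and it can be as little as 11%.
- That an MI sensitivity result for EASI 100 will be NRI in disguise. No such analysis is planned: SAP 9.4.3 has none for ranked endpoints, and the MI seeds cover the primary endpoint only.
- That the bias is always conservative. That needs similar missingness by arm.
- That the sample code confirms under-counting. Its EASI 90 cut-off does the opposite.

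The bounds also appear only in the sample code. If out-of-range draws were set to 0 instead of redrawn, EASI 100 would be over-produced (24% vs 15% true on upadacitinib, 15% vs 5% on dupilumab). That reading changes the direction of the error and does not remove it.

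**Conclusion.** The point holds for values handled by MI. With redrawing, the model gives EASI 100 in about 0-1% of imputations whatever the true rate, and under-imputes EASI 90 as the text defines it, often by half. This is a fault of the imputation model and arises even when MAR is true.

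The consequence is modest: roughly 0.6-1.5 points on the EASI 90 difference and 0.9 points on the EASI 100 difference per 10% imputed, and about 1 point of power. The primary conclusion is unlikely to change. I have not calculated the effect on the primary composite itself, nor any effect for WP-NRS. The EASI 100 result rests on the redraw assumption and hardly at all on the EASI distribution; the EASI 90 sizes rest on both. The change is worth making because it is cheap and because the MI sensitivity analysis should not inherit the flaw.

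**What to change.** In SAP Appendix H, 2.2, 2.3 and 3.0, and the matching text in Section 9.2, replace both the MCMC augmentation and the monotone regression step for EASI and regional EASI with a single FCS REGPMM step (predictive mean matching) using the same covariates. Imputed values are then observed scores, including 0.

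Changing only the monotone step to REGPMM is not enough, because intermittent gaps would still receive normal draws from the MCMC step; this bears on the Week 2 and Week 4 endpoints. If the MCMC step is kept for those gaps, keep its MIN, MAX and ROUND settings.

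Separately, reconcile the sample code's EASI 90 cut-off (at most 0.9 × Baseline) with the 90% reduction in the text. Predictive mean matching does not correct that.

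Cost: a few SAP passages and the code are rewritten, and there is slightly more Monte Carlo variation where donors are few.

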### **2.3 Imputation Algorithm**

It is reasonable to assume the missing values of the longitudinal data for an outcome variable (e.g., EASI, the original scale of EASI 90, at each post-baseline visit) follows a monotone missing pattern. In practice, the missing data of the outcome variable might have an arbitrary (non-monotone) missing data pattern. An extra step may be added accordingly, to augment data into a monotone missing pattern.

For the outcome variable (e.g., EASI at each visit), K 'complete' datasets can be generated in two steps: augmentation step and imputation step. K, the number of repetitions, is determined below.

#### **Augmentation Step**

For datasets with non-monotone missing data pattern, the augmentation step will first impute enough values to augment the data into a monotonic missing pattern:

Markov Chain Monte Carlo (MCMC) will be applied to augment the data using PROC MI with the MCMC IMPUTE monotone statement, assuming a multivariate normal distribution. The augmented data will be used in the subsequent imputation step to generate 'complete' datasets. Covariates included in the model are treatment, stratification factors (vIGA-AD categories (vIGA-AD 3; 4) and age (12 to < 18; 18 to < 40;  $\geq 40$  to < 64 years)), Baseline, and all post-baseline visits of the outcome variable according to the pre-specified order. Of note, categorical variables are included using the form of dummy variables.

Repeat the imputation process K 30 times using the procedure described above to form K 30 monotone missing datasets, where K is determined as described in "Repetition of Imputations (K)."

### **Imputation Step**

For missing data with monotone missing patterns, the choice of multiple imputation using a parametric regression model that assumes multivariate normality is appropriate.

The imputation step is described below:

The imputation model for the missing data is a regression model, which controls for treatment, stratification factors (vIGA-AD categories [vIGA-AD 3; 4]) and age (12 to < 18; 18 to < 40;  $\geq$  40 to < 64 years), Baseline, and all post-baseline visits of the outcome variable. The covariates included in the model and the order of these variables are consistent with the augmentation step.

For each monotone missing dataset, using SAS PROC MI with MONOTONE REG model statement, the outcome variable at each post-baseline visit with missing values will be imputed sequentially with covariates constructed from their corresponding sets of preceding variables.

A 'complete' dataset with imputed values for the missing data is generated after the augmentation and imputation steps are completed.

